7.3. MEDICAL HISTORY AND CONCOMITANT DISEASES

Medical history including any past and/or concomitant diseases or past surgeries will be collected at baseline. All terms will be coded using MedDRA Version 18.0 and summarized by System Organ Class (SOC), preferred term, and treatment group.

Medical history data will also be listed. Medical history data will be summarized using the Efficacy and Safety Populations.

7.4. PRIOR AND CONCOMITANT MEDICATION

Medications will be classified using the current version of the World Health Organization Drug Dictionary Enhanced, B2 Format (March, 2015). Individual data listings will be presented for each subject, with separate listings for prior medications and concomitant medications. In addition, concomitant medications will be summarized by Anatomical Therapeutic Chemical (ATC) classes and PT using frequency counts and percentages. For the summaries of concomitant medications, subjects who take the same medication (in terms of the preferred term) more than once will be counted only once for that medication. Prior medications will be summarized separately in a fashion similar to concomitant meds.

Prior and concomitant medication data will be summarized using the Efficacy and Safety Populations.

7.4.1. Prior Medication

Prior medications are medications that were stopped ≥ 28 days prior to screening visit.

7.4.2. Concomitant Medication

Concomitant medications are any medications started between 28 days prior to Screening through the End of Study visit.

Amendment Final V 2.0

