5. Other therapies for NAFLD or NASH: requires a stable regimen for at least 3 months prior to the Screening biopsy of record and throughout the study. May include vitamin E, milk thistle, thiazolidinediones and pentoxifylline.

Double-Blind Cohort:

Includes statins.

Open-Label Single Blind and Placebo Controlled 24 Week Histology Cohorts:

Includes statins if the conditions below are met. Other therapies may include vitamin E ( $> 800$  IU Placebo cohort only), milk thistle, thiazolidinediones (open-label, single-blind only) or pentoxifylline.

- a. Patient can be defined as statin naïve or experienced at Screening based on the following definitions:
  - i. **Statin-naïve:** no administration of statins within 3 months prior to enrollment.
  - ii. **Statin experienced:** administration of  $\leq 50\%$  of the maximal dose of current statin therapy.
- b. Requires a stable regimen for at least 3 months prior to Screening through Week 2.

The following are the acceptable daily doses of approved statin therapies, including combination preparations of statins and other lipid lowering agents. Also listed under Concomitant Medications in [Section 9.7](#).

- Atorvastatin:  $\leq 40$  mg/d
- Fluvastatin:  $\leq 40$  mg/d
- Lovastatin:  $\leq 40$  mg/d (immediate release),  $\leq 30$  mg/d (extended release)
- Pitavastatin:  $\leq 2$  mg/d
- Pravastatin:  $\leq 40$  mg/d
- Rosuvastatin:  $< 20$  mg/d (Note: must be  $<$  not  $\leq$  20 mg/d)
- Simvastatin:  $\leq 40$  mg/d

6. The following liver enzyme parameters must be met at Screening:
  - a. ALT and AST  $\leq 250$  IU/L
  - b. Abnormal ALT defined as:  $\geq 30$  IU in males and  $\geq 19$  IU in females
  - d. AST  $\geq 30$  IU/L except for patients with a historical biopsy within 3 months of screening with NAS of at least 4 with 1 point in each component and fibrosis stage 2 or 3 (Placebo-Controlled Cohort only)
7. The following additional laboratory parameters must also be met at Screening:

- a. Total bilirubin must be within normal range. For patients diagnosed with Gibert's Syndrome, please contact medical monitor/designee
  - b. INR  $\leq$  1.3 (in the absence of warfarin or other anticoagulant therapy)
  - c. Creatinine clearance  $\geq$  90 mL/min as calculated by Cockcroft-Gault equation
  - d. Alpha fetoprotein (AFP)  $<$  100 ng/mL
  - e. LDL C  $\leq$  185 mg/dL (except Double-blind cohort and  $\leq$  165 mg/dL for the Open-Label Single Blind )

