## 9.7 Prior and Concomitant Medications

Concomitant therapies are any prescription or over-the-counter preparations used by a subject while participating in this study and must be recorded from 28 days prior to Day 1 until end of study.

Subjects should refrain from the use of any new medications or products or change in the dose or frequency of existing therapies during Screening and throughout the study. The Medical Monitor should be informed of any changes or addition of medications during this time period.

**Prohibited Medications** from 28 days prior to Day 1 and throughout study:

- Investigational agents, other than NGM282, or devices for any indication
- Known hepatotoxic agents
- Agents used for the treatment of any condition listed in the exclusionary enrollment criteria (see [Section 8.1.2](#))
- Any hepatotoxic herbal medications other than standard vitamin supplements

Placebo-Controlled 24 Week Histology Cohort Only:

- Investigational agents, other than NGM282, or devices for any indication
- Agents used for the treatment of any condition listed in the exclusionary enrollment criteria (see [Section 8.1.2](#))
- Hepatotoxic agents outlined in ([Appendix E](#)).
  - All other hepatotoxic agents will be left to the discretion of the PI. There should be clear documentation in the patient study records of PI approval of use.

**Prohibited Medications** within 3 months of Screening and throughout study:

- Ezetimibe, colesevelam, cholestyramine, niacin, PCSK9 inhibitors, or other lipid-lowering agents (except Double-blind)

Placebo-Controlled 24 Week Histology Cohort Only:

- Contraindicated medications according to rosuvastatin package insert ([Appendix C](#))
  - Includes cyclosporine, gemfibrozil, protease inhibitors (atazanavir, ritonavir, lopinavir, simeprevir), coumarin anticoagulants, fenofibrates, niacin and colchicine
- Contraindicated medications according to ezetimibe package insert ([Appendix D](#))
  - Includes cyclosporine, fenofibrate, cholestyramine and coumarin anticoagulants

- Use of any other lipid lowering agents or combination preparation of statins, within 3 months of Screening and throughout study, **except** ezetimibe when approved by MM/designee as second line lipid management therapy.
  - colesevelam, cholestyramine, niacin, PCSK9 inhibitors (evolocumab or alirocumab), colestid, fibrates, fenofibrates, pharmacologic/prescribed fish oil

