#### **12.10.8 Concomitant Medications**

Concomitant medications will be classified using the current version of the World Health Organization Drug Dictionary Enhanced (2012). Concomitant medications are medications taken at least once from 28 days prior to Screening through the End of Study visit.

Medications stopped on the 28 days prior to Screening time point will not be considered a concomitant medication.

Individual data listings will be presented for each subject, with separate listings for prior medications and concomitant medications. In addition, concomitant medications will be summarized by Anatomical Therapeutic Chemical (ATC) classes and PT using frequency counts and percentages. For the summaries of concomitant medications, subjects who take the same medication (in terms of the preferred term) more than once will be counted only once for that medication.

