6.3. MISSING DATA

Subjects who discontinue the study prematurely will not be replaced. No imputation will be made for missing data. All analyses will be based on available data, unless otherwise stated. Subjects Incomplete or missing data will be presented in the listings as they were reported on the CRFs.

Missing or incomplete dates for AEs and concomitant medications will be imputed as needed only to determine treatment emergence or distinguish between prior and concomitant medications.

If an AE has a missing onset date, then the AE will be considered a TEAE unless a non-missing stop date indicates otherwise. A medication with a completely missing start date will be considered a prior medication. A medication with a missing stop date will be considered a concomitant medication.

If an AE or a medication has a partial start or stop date, the following rules will be used to determine whether it is an AE or a TEAE, a prior or a concomitant medication.

Date imputation rules for medications and adverse events are summarized in Table 1.

Table 1 Imputation of Missing Dates

Partial Missing Start or Stop Date	Imputed Start Date	Imputed Stop Date
Missing month and day but the year is present	January 1 of that year or first dose date if the year is the same as the first dose date	December 31 of that year
Missing day but the year and month are present	First day of that month or first dose date if the year and month are the same as the year and month of first dose date.	Last day of that month

Amendment Final V 2.0

Note: If the imputed start date is after the stop date, then the start date will be set to equal the stop date.

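### SAP 7.4.2 defines concomitant medication by start date where the protocol defines it by use, so a long-standing drug stopped after the 28-day cut-off is neither prior nor concomitant (minor)

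*SAP*

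**What the plan says.** The SAP covers the placebo-controlled 24-week histology cohort and splits medications with two definitions that rest on different dates.

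- SAP 7.4.1 uses the stop date: "Prior medications are medications that were stopped ≥ 28 days prior to screening visit".
- SAP 7.4.2 uses the start date: "Concomitant medications are any medications started between 28 days prior to Screening through the End of Study visit".
- SAP 6.3 adds rules for missing dates. On the start date it says: "A medication with a completely missing start date will be considered a prior medication". A missing stop date makes a medication concomitant.
- SAP 7.4 promises separate listings and separate summaries for the two classes. SAP 11, on changes from the protocol's analysis, reads NA.

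The protocol classifies by use. Section 12.10.8 says: "Concomitant medications are medications taken at least once from 28 days prior to Screening through the End of Study visit". It then sets the boundary: "Medications stopped on the 28 days prior to Screening time point will not be considered a concomitant medication". Section 9.7 also speaks of use: "Concomitant therapies are any prescription or over-the-counter preparations used by a subject while participating in this study". However, it requires recording from 28 days before Day 1, not before Screening.

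Eligibility determines how long background drugs have been in use. For statins, protocol 8.1.1 item 5 says: "Requires a stable regimen for at least 3 months prior to Screening through Week 2". For this cohort, item 4 requires diabetes drugs to be stable for at least 3 months, and GLP1 agonists and pioglitazone for at least 12 months, before Day 1 and throughout the study. Other NASH therapies must be stable for at least 3 months before the Screening biopsy of record and throughout.

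**The concern.** A start-date test for one class and a stop-date test for the other do not cover every drug. A medication that began before the cut-off and was still being taken after it passes neither test. The eligibility rules push background statin, diabetes and NASH therapy into that position, because a stable regimen must have begun months earlier.

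A program that follows the SAP literally could leave such drugs out of both tables and both listings. These are the drugs a reader would want to see by arm when judging liver fat, ALT and LDL-C. The protocol synopsis also names the prevalence of concomitant medications under safety and tolerability.

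**Working it through.** The plan gives no figure to reproduce. The check applies the date rules to drugs that just meet the eligibility minimum.

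**Inputs.** The cut-off is 28 days before Screening (SAP 7.4.1 and 7.4.2). Screening is taken at 14, 28 or 42 days before Day 1: protocol 9.5 and Table 4 ask for at least 14 days' separation, and the normal 28-day window may be extended to 42. Three months is taken as about 90 days and 12 months as about 365 days (assumptions). The statin period runs from Screening. The diabetes-drug, GLP1-agonist and pioglitazone periods run from Day 1.

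**Formulas.** Cut-off, in days before Day 1 = Screening + 28. Latest permitted start of a drug whose period runs from Day 1, in days before the cut-off = 90 or 365 minus the cut-off. For a statin it is 90 − 28.

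| Screening (days before Day 1) | Cut-off (days before Day 1) | Diabetes drug: start before cut-off | GLP1 agonist or pioglitazone | Statin |
|---|---|---|---|---|
| 14 | 14 + 28 = 42 | 90 − 42 = 48 | 365 − 42 = 323 | 90 − 28 = 62 |
| 28 | 28 + 28 = 56 | 90 − 56 = 34 | 365 − 56 = 309 | 62 |
| 42 | 42 + 28 = 70 | 90 − 70 = 20 | 365 − 70 = 295 | 62 |

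Every entry is positive, so each of these drugs started before the SAP 7.4.2 window opens. NASH therapies are at least as early as diabetes drugs, because the biopsy of record precedes Day 1.

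**Classification.** The result is the same at all three Screening days.

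| Medication record | Prior, SAP 7.4.1 | Concomitant, SAP 7.4.2 | SAP 6.3 | Concomitant, protocol 12.10.8 |
|---|---|---|---|---|
| Statin begun 90 days before Screening, stopped at Week 2 | no | no | no missing date | yes |
| Older drug stopped at Screening | no | no | no missing date | yes |
| Diabetes drug, GLP1 agonist or pioglitazone, ongoing | no | no | concomitant, if ongoing means missing stop date | yes |
| Older drug stopped 40 days before Screening | yes | no | no missing date | no |
| Drug begun 10 days before Screening, ongoing | no | yes | concomitant, if ongoing means missing stop date | yes |
| Start missing, stopped on study | no | cannot be judged | prior | yes |
| Both dates missing | cannot be judged | cannot be judged | prior and concomitant | cannot be judged from dates |

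The first two rows are the gap that no other SAP rule closes. The protocol itself creates the first: its Week 2 and Week 4 procedures for this cohort (9.6.3, 9.6.4) include switching to rosuvastatin, which gives the baseline statin a recorded stop date on study.

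The last two rows are separate faults in SAP 6.3. A drug stopped on study is sent to prior, against SAP 7.4.1. A drug with neither date receives both classes, with no order of precedence.

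**Recording window.** The protocol 12.10.8 window opens 42 to 70 days before Day 1, and protocol 9.7 requires recording from 28 days before Day 1. Recording is therefore required only from 14 (42 − 28) to 42 (70 − 28) days after the classification window opens.

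**The case against.** The strongest reply is that SAP 6.3 already deals with most of this. Diabetes drugs, GLP1 agonists, pioglitazone and NASH therapies must stay stable throughout the study, so a compliant subject has no stop date, and a missing stop date makes the drug concomitant. Much of this stands. A reader might infer that long-standing background drugs as a class vanish from both tables, but the documents do not support that. What they show is that ongoing drugs depend on an unstated coding convention, and that SAP 6.3 cannot reach a drug whose dates are complete.

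A reader might also infer that arm balance can no longer be judged. That is too strong. SAP 7.2 tabulates statin status and type 2 diabetic status by treatment group, and study rosuvastatin has its own administration and exposure listings. What can be lost is drug-level detail.

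Nor do the documents allow a count of affected subjects. They give no statin-experienced share for this cohort and no switching rate. Switching depends on LDL-C results on study, and continuing current therapy is an explicit option.

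Finally, the safety-endpoint argument is weaker than the synopsis suggests. SAP 4.4 and protocol 12.10 do not list concomitant medications among the safety parameters, and no inferential analysis described uses this classification. The start-date wording may be a drafting slip. It is nevertheless the stated rule, and SAP 11 does not present it as a deliberate change.

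**Conclusion.** The point holds in limited form, as a minor one. As written, SAP 7.4.1 and 7.4.2 leave unclassified any drug begun more than 28 days before Screening with a recorded stop date after that cut-off. Protocol 12.10.8 would count it as concomitant. A baseline statin replaced by study rosuvastatin is the clearest example. Ongoing background drugs are covered only if ongoing use is stored as a missing stop date. SAP 6.3 also misplaces a drug with a missing start date that was stopped on study, and contradicts itself when both dates are missing.

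The consequence is confined to the descriptive medication tables and the prior/concomitant split of the listings. It does not touch the primary analysis, power or the SAP 7.2 baseline summaries.

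The gap itself follows from the wording alone. Its reach to drugs at the eligibility minimum rests on 3 months being about 90 days, 12 months about 365 days, and Screening falling 14 to 42 days before Day 1. The smallest margin is 20 days, so rounding the months differently by a few days would not change it.

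**What to change.** 1. Replace the SAP 7.4.2 definition with the protocol 12.10.8 rule: any medication taken at least once from 28 days before Screening through End of Study, whatever its start date.
2. State in SAP 7.4.2 that a medication recorded as ongoing is concomitant.
3. Change SAP 6.3 so that a missing start date means concomitant unless the stop date is at least 28 days before Screening. This also settles the case where both dates are missing.
4. Reconcile the window with protocol 9.7, which records from 28 days before Day 1, and say which window the tables use. If the Screening-based window stays, the early part may not be fully recorded.

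With the protocol wording, every fully dated or ongoing drug in the check above falls into exactly one class. One consequence should be accepted knowingly: a drug stopped 20 days before Screening counts as concomitant although it was never taken with study drug.

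The cost is a few sentences in the SAP and one programming condition, plus a decision on the recording window. It needs no change to the primary analysis or the sample size.

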8. EFFICACY AND PHARMACODYNAMIC (PD) ENDPOINTS

8.1. PRIMARY EFFICACY ENDPOINT AND ANALYSES

The primary efficacy endpoint for this study will be the change in liver fat content as measured by MRI PDFF in subjects with histologically confirmed NASH after 24 weeks of treatment. The analyses for this primary endpoint are detailed in the previous SAP for double-blind phase.

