## 12.2 Randomization and Enrollment

For the double-blind cohort, at Day 1 all eligible subjects will be randomized via IWRs to one of the three treatment arms (NGM282 3 mg, NGM282 6 mg, or placebo) in a 1:1:1 ratio. The proportion of subjects with diabetes (categorized on a dichotomous scale) will be balanced across the three groups to ensure an even distribution across the three groups.

Diabetes status for balancing (“no diabetes” or “diabetes”), will be based on medical history, Screening labs, current medications, and clinical assessments.

The single-blind cohort is not randomized. Subjects will initially be enrolled sequentially into dosing Group 1 and enrollment will be continuous within and between each dosing groups. Sequencing of the dosing Groups 2 and 3 will be based on PD and safety parameters from dosing Group 1 and may run in parallel to each other. A fourth optional dosing group may be conducted based on the safety/tolerability, imaging data and histology (dosing Group 3 only) data from the prior 3 dosing groups. Dosing Group 4 will be initiated only after all subjects in Cohort 3 have been enrolled and a minimum of 10 subjects have completed 12 weeks of treatment in order to do a preliminary review of key data. Dosing group sequence and individual subject treatment assignment will be blinded only study subjects throughout the study period.

For the placebo-controlled 24-week histology cohort, at Day 1 all eligible subjects will be randomized via IWRS to one of the two treatment arms (NGM282 1 mg or placebo) in a 2:1 ratio. The Sponsor, study sites, and subjects will be blinded to treatment assignment. The randomization schedule will be stratified by subject’s fibrosis stage 2 or 3 based on the screening qualification liver biopsy.

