## 12.9.2 Analysis of Primary Endpoint

The analysis of the primary endpoint will be based on the Efficacy population.

The absolute change in liver fat content from Baseline to EOT will be compared between treatment groups using an analysis of covariance (ANCOVA) model with treatment group and diabetic status (double-blind cohort only) as cofactors and Baseline endpoint as a covariate. Least square means with standard errors (SEs), differences in least square means with SE, 95% CIs for the difference in least square means, and corresponding p-values will be presented. Further covariates/cofactors may be included in the modeling depending on the relevance to the endpoint analyzed and will be further described in the SAP.

In cases where the parameters do not follow a normal distribution, a non-parametric approach will be followed to analyze the difference between treatment groups.

The primary analysis for the primary endpoint will be repeated for the Per Protocol population.

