2. PURPOSE

The purpose of this statistical analysis plan (SAP) is to ensure that the data listings, summary tables and figures which will be produced, and the statistical methodologies that will be used, are complete and appropriate to allow valid conclusions regarding the study objectives. This SAP only describes the analysis to be conducted on the placebo-controlled 24-week histology cohorts of this trial. The analysis of pharmacokinetics (PK) data will be provided in a separate report and will not be included in this SAP.

The planned analysis for each phase of the study (double-blind, open-label, and placebo-controlled) will be detailed in separate analysis plans.

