4.2. SECONDARY EFFICACY ENDPOINTS

- The actual and percentage change from Baseline in liver fat content by MRI-PDFF at Weeks 6, 12, 24, and 30.
- The percentage of normalization in liver fat content at EOT.
- The percentage of responders
 - a liver fat content decrease $\geq 5\%$
 - a liver fat content relative decrease by $\geq 30\%$
- The actual and percentage changes from Baseline to EOT as well as the percentage of normalization of AST, ALT, bilirubin (total, direct), triglycerides and GGT. Percentage of normalization by Week 24 will be investigated for these parameters (including clinically meaningful normalization of Triglycerides)
- The actual and percentage changes from Baseline to EOT of the following parameters: Total cholesterol, HDL-cholesterol, LDL-cholesterol, and lipoprotein particles.
- The actual and percentage changes from Baseline to EOT of the following parameters: [REDACTED], Pro-C3, ELF Score, Fasting blood glucose, insulin levels, HbA1c, [REDACTED], and HOMA-IR, Body weight, BMI, and waist circumference, C4 and serum bile acids, Bile-mediated absorption as measured by fat-soluble vitamins and fecal fat content.
- The percentage of liver histologic responders
 - Improvement in liver fibrosis by ≥ 1 stage by NASH Clinical Research Network (CRN) criteria with no worsening of steatohepatitis
 - Resolution of NASH (defined as an NAS score of 0 or 1 for inflammation and 0 for ballooning) with no worsening of fibrosis as determined by the NASH CRN criteria.

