8.2. SECONDARY EFFICACY/PD ENDPOINT(S) AND ANALYSES

The main analysis population for secondary efficacy endpoints is the Efficacy Population. The analysis will also be repeated for the Per Protocol population and for subjects who completed their Week 24 assessment (completers) only.

8.2.1. The actual and percentage change from baseline in liver fat content by Magnetic Resonance Imaging-proton Density Fat Fraction. MRI-PDFF at Weeks 6, 12, 24, and 30

The observed values and changes from baseline will be summarized at Weeks 6, 12, 24, and 30, by NGM282 treatment group and fibrosis stage. The actual change and percentage change in absolute liver fat content from baseline to Week 6, Week 12, Week 24 and Week 30 will be compared between treatment groups using an analysis of covariance (ANCOVA) model with treatment group and fibrosis stage at baseline as cofactors and baseline endpoint and baseline ALT as covariates. Least square means with standard errors (SE), differences in least square means with SE, 95% CIs for the difference in least square means, and corresponding p-values will be presented.

The assumptions of normality will be evaluated. If the assumptions of normality are not satisfied, a rank ANCOVA method will be performed in addition to the parametric model.

The rank ANCOVA is a non-parametric statistical method described in Stokes, Davis, and Koch, 2000. It can be considered as an extension to the Wilcoxon rank-sum test with the ability to adjust for covariates and cofactors in the model. The mean, median and p-value for the actual change will be presented.

8.2.2. The percentage of normalization in absolute liver fat content at Week 24

Normal liver fat content normalization will be defined as $\leq 5.0\%$. Percent of subjects with normalized liver fat content will be presented by treatment group and fibrosis stage and will be analyzed through a chi-square test. The difference between proportions observed in each treatment group, along with 95% CIs for the difference between proportions, will be presented for all pairwise comparisons of treatment

Amendment Final V 2.0

groups. Fisher exact test will be used if 50% of the cells have expected counts less than 5.

8.2.3. The percentage of responders (based on a liver fat content decrease $\geq 5\%$, and relative decrease $\geq 30\%$)

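### SAP 8.1 states no model for the 24-week cohort's primary endpoint, while SAP 8.2.1 tests the same Week 24 PDFF change as secondary with a model that differs from the one protocol 12.9.2 implies.

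*SAP*

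**What the plan says.** SAP 4.1 makes the actual change in MRI-PDFF liver fat after 24 weeks the primary endpoint. On its analysis, SAP 8.1 says only: "The analyses for this primary endpoint are detailed in the previous SAP for double-blind phase". The section is not redacted. SAP 2 limits this plan to the 24-week cohort and adds: "The planned analysis for each phase of the study (double-blind, open-label, and placebo-controlled) will be detailed in separate analysis plans".

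SAP 4.2 then lists as secondary: "The actual and percentage change from Baseline in liver fat content by MRI-PDFF at Weeks 6, 12, 24, and 30". SAP 8.2.1 analyses these changes by an ANCOVA "model with treatment group and fibrosis stage at baseline as cofactors and baseline endpoint and baseline ALT as covariates". If normality fails, "a rank ANCOVA method will be performed in addition to the parametric model".

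Protocol 12.9.2 gives the primary ANCOVA with "treatment group and diabetic status (double-blind cohort only) as cofactors and Baseline endpoint as a covariate". It lets the SAP add covariates. If normality fails, "a non-parametric approach will be followed to analyze the difference between treatment groups".

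Protocol 12.2 stratifies this cohort's randomisation by "fibrosis stage 2 or 3 based on the screening qualification liver biopsy". SAP 11, on changes from the protocol, says NA.

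**The concern.** The pointer leads to the plan for a three-arm, 12-week cohort that protocol 12.2 balances on diabetic status. The 24-week cohort has two arms and is stratified by fibrosis stage. The model that protocol 12.9.2 leaves for it has no term for that stratum. The model that does have one stands only under the secondary heading.

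At stake is whether the primary result is fixed in advance. If two models can each be presented as the planned one, the choice can be made after the data are seen. Protocol 12.12 also plans an interim review of selected efficacy endpoints by treatment group. It does not say whether PDFF is among them, but it is a further reason to fix the model in writing first.

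**Working it through.** **The two documented specifications for Week 24 actual PDFF change**

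| | Model A (protocol 12.9.2, by implication) | Model B (SAP 8.2.1) |
|---|---|---|
| Label | primary | secondary |
| Factors | treatment | treatment, fibrosis stage |
| Covariates | baseline PDFF | baseline PDFF, baseline ALT |
| If not normal | non-parametric approach replaces the ANCOVA | rank ANCOVA added to it |

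**The plan's own sample size**

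Inputs from protocol 12.1 and SAP 3.5: 15% against 50%, 80% power, alpha 0.05, 2:1, 15% drop-out.
- Pooled rate = (0.15 + 2 × 0.50)/3 = 0.3833.
- Placebo n = [1.96 √(0.3833 × 0.6167 × 1.5) + 0.8416 √(0.15 × 0.85 + 0.50 × 0.50/2)]² / 0.35² = (1.167 + 0.423)² / 0.1225 = 20.6, so 21.
- Total = 21 + 42 = 63. Then 63/0.85 = 74.1, so 75, as stated.

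The size rests on histologic response. No PDFF model enters it.

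**Cost of the extra covariates when they explain nothing**

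With 42 against 21 evaluable, SE = SD × √(1/42 + 1/21) = 0.267 × SD. At a 5-point difference the noncentrality is 5/(0.267 × 5) = 3.74 for SD 5 and 5/(0.267 × 8) = 2.34 for SD 8. Residual degrees of freedom are 60 for A and 58 for B. Power is 95.7% for both at SD 5, and 63.4% against 63.3% at SD 8. The lost degrees of freedom cost almost nothing. Chance imbalance in the covariates adds a little, which the simulation below picks up.

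**Effect of having two models**

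Settings: 30,000 simulated trials each, 63 subjects, 2:1 in permuted blocks of 3 within fibrosis stratum, normal errors. SD 5 to 8 is borrowed from the double-blind power table in protocol 12.1. Three inputs are assumptions that the documents do not give:
- half the subjects at stage 3;
- half the subjects diabetic;
- effects of fibrosis stage, ALT (per SD) and diabetes all 0, all 1 or all 2 points of liver fat.

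Results with 5 to 8 as residual SD:
- No true difference: A alone 4.6% to 5.2%, B alone 4.8% to 5.1%, either one significant 5.4% to 6.5%.
- True difference 3 points: power 26.2% to 59.0% for A and 27.2% to 58.3% for B. B minus A is −0.7 to +6.2 percentage points. The two disagree on significance in 3.1% to 13.5% of trials.
- True difference 5 points: B minus A is −0.9 to +3.8.

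A second run with new random numbers gave 5.5% to 6.4% for either model, and −0.9 to +6.5 at 3 points. Hence the rounded −1 to +7.

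If 5 to 8 is read instead as the SD of change, with an assumed correlation of 0.5 with baseline, either-model error is 5.4% to 6.9%. B minus A at 3 points is −0.9 to +11.3, the top value coming from SD 5 with all effects at 2.

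**Hand check of the largest residual-SD gain** (SD 5, effects 2, difference 3). A binary factor with half in each group and effect 2 adds 4 × 0.25 = 1 to the variance; ALT adds 4.
- B omits only diabetes: residual variance 25 + 1 = 26, noncentrality 3/(0.267 × 5.10) = 2.20.
- A omits all three: 25 + 1 + 4 + 1 = 31, noncentrality 3/(0.267 × 5.57) = 2.02.

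This agrees in direction and rough size with the simulated gain.

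**The case against.** The best defence is that the protocol already settles the matter. Section 12.9.2 implies a model for this cohort and lets the SAP add covariates, and SAP 8.2.1 adds them for exactly this variable and week. Protocol 12.9.3 stratifies this cohort's secondary analyses by fibrosis stage. All of this points to the SAP 8.2.1 model as the intended one, and that much stands. But the additions appear only under the secondary heading, SAP 8.1 sends the primary analysis elsewhere, and SAP 11 declares no change. The unseen double-blind SAP might contain a section for this cohort. Even so, SAP 8.2.1 would still test the same contrast as secondary.

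The second defence is that little depends on it. Protocol 12.3 states a PDFF hypothesis only for the double-blind cohort, protocol 12 calls the general approach descriptive, and the covariate effects above are assumed. This stands and limits the weight of the point.

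Three stronger readings are tempting, and the documents do not support them.
- A reader might infer a third candidate model with diabetic status. Protocol 12.9.2 restricts that factor to the double-blind cohort, and the SAP pointed to cannot be checked.
- A reader might see two definitions of baseline ALT, because footnote j of protocol Table 4 takes a median of Screening and Day 1. The SAP's version of that footnote ties the median to the liver-safety criterion of protocol 8.2. The general definitions in protocol 12 and SAP 6.2.1 both use the last pre-dose value.
- A reader might take SAP 5.3, which asks for a dose of NGM282, to exclude placebo subjects. SAP 8.2 compares treatment groups, so this is a drafting slip and not a second analysis.

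**Conclusion.** The point holds. This SAP specifies no primary model for its own cohort. The same Week 24 contrast is primary under a protocol model that omits the randomisation stratum and secondary under a SAP model that includes it. No text says which result, or which test under non-normality, decides.

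The size is modest: about 5% error for either model alone and about 5.3% to 7% if either may be claimed. The SAP 8.2.1 model moves power by about −1 to +7 percentage points at a true 3-point difference. This rests on 42 against 21 evaluable, residual SD 5 to 8 borrowed from another cohort, and assumed covariate effects of 0 to 2 points. With no covariate effects the SAP 8.2.1 model gains nothing and loses under one point. The planned 75 subjects stand. Neither model is invalid; the fault is that the primary test is not unique.

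**What to change.** Before unblinding:

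- **SAP 8.1:** replace the pointer with one ANCOVA for Week 24 actual PDFF change. Factors: treatment and fibrosis stage. Covariates: baseline PDFF and baseline ALT as defined in SAP 6.2.1. Two-sided 5%, Efficacy population, repeated in Per Protocol.
- **Fibrosis stage:** state that it means the randomisation stratum (2 or 3, from the qualification biopsy, protocol 12.2). SAP 8.2.1 refers only to stage at baseline, and protocol 9.9.1 has a central reading of the Screening biopsy reported separately, so the two could differ.
- **SAP 4.2 and 8.2.1:** remove Week 24 actual change from the secondary list; keep percentage change and the other weeks.
- **Non-normality:** state that the parametric ANCOVA decides and the rank ANCOVA is supportive.
- **SAP 11:** record that rule and the added covariates as departures from protocol 12.9.2.
- **SAP 5.3, as a separate wording correction:** change NGM282 to study drug, to match protocol 12.4.4.

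The cost is SAP wording only: no new data, no extra visits and no change in sample size.
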